1.0 Objectives

Our objective is to examine the feasibility and acceptability of a home-based lifestyle activity intervention to promote light-intensity activity and reduce sedentary activity using a whole-of-day approach. Sixty-four older cancer survivors will be randomized to either a 12-week theory-based intervention or a waitlist control. The intervention uses a wearable activity tracker that pairs with a smartphone app to promote awareness and enable self-monitoring of both activity and inactivity. Motivational counseling will be used to individually tailor strategies to achieve goals. Data will be collected at baseline, post-intervention, and 3-months post-intervention. We will pursue the following specific aims.

1.1 Primary Aims and Hypotheses

1.1.a. Determine the feasibility and acceptability of a home-based lifestyle activity intervention by assessing recruitment, retention, adherence rates, and participant satisfaction, and monitoring adverse events. We hypothesize that we will meet the accrual target of older cancer survivors within 18 months, retain 80% of the sample, and achieve 80% adherence/fidelity to the intervention with high satisfaction ratings, while limiting the number of adverse events.

1.1.b. Estimate effect sizes for primary and secondary endpoints for the adoption (baseline to 12 weeks) and maintenance (3-months post-intervention) of the intervention. We hypothesize that compared to the control condition, the intervention will result in improvements in physical function (primary outcome) and secondary outcomes: physical performance, objective measures of sedentary- and light-intensity activities, and self-reported quality of life. Further, we hypothesize that the arm differences at 12 weeks will be sustained at 3-months post-intervention.

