- Not currently participating in a program (personal, e.g., wearing an activity monitor, or structured, e.g., another study) to decrease sedentary time or increase physical activity.
- Not planning to move out of New Mexico within the next year.
- Own a smartphone, tablet or computer OR be willing to use a study provided smartphone capable of running the Fitbit app or website. Additionally, access to the internet or a Wi-Fi hotspot at least once per week is required. Smartphones and data plans will be provided to those individuals who are eligible but do not currently own a computer, tablet or smartphone. Participants loaned a study phone will be asked to sign form indicating they agree to return the phone at the end of the study.
- Availability of a family member or friend to be present (for safety) during remote assessment of physical performance tests.
- Willingness to be randomized to either study arm and to wear activity trackers (activPAL3 [sedentary behavior, standing, stepping] at weeks 1, 13, and 26 for 7 days; the Fitbit activity tracker during weeks 2-26 during waking hours if randomized to the immediate intervention arm; during weeks 14-26 if randomized to the delayed intervention arm).

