Lifestyle Activity Intervention: The goal of the intervention is to be more active throughout the day, every day – a whole-of-day approach - without regard for frequency, intensity, or duration of activity bouts. To promote gradual and sustained change, participants will be asked to increase the number of steps per day (above their individual baseline level) during weeks 3-12, and then work to maintain their goals during weeks 13-25 (**Table 3**). The target of 3,000 extra steps per day represents approx. 30 extra minutes of LPA,⁴⁵ which is associated with health benefits.^{27,46} To encourage activity throughout the day (and reduce SB), participants will work towards 10 of 14 active hours per day (defined as >250 steps/hour in Fitbit). Frequent interruption of sitting is associated with better cardiometabolic health.^{21,47-49} In accordance with SDT and MI, participants will choose their own strategies for becoming more active and achieving their weekly goals with guidance and (technology) support from their health coach. A menu of ideas will be provided in their education materials, but participants will be encouraged to identify options that work best for their lifestyle.

Table 3. Intervention Schedule			
Week	# Active Hours/day	Steps/day (above baseline)	Minimum # days / week
1	Baseline assessment randomization, Fitbit mailed to participant		
2	Establish Fitbit baseline data		
3-4	6	1000	3,5
5-6	7	1500	3,5
8-8	8	2000	3,5
9-10	9	2500	3,5
11-12	10	3000	3,5
13	Post-intervention assessment		
14-25	Maintain goals (no study contact)		
26	3-months post-intervention assess.		

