Educational Materials: Participants will be mailed educational materials (visual aids) to be used during the telephone calls with their Health Coach. The handouts include: (a) the benefits of LPA and suggestions for how to add more steps to their day, throughout the day (i.e., breaking up sedentary time through at least minimal stepping each hour); (b) reasons to be physically active; (c) example plans for meeting step goals; (d) ideas for getting more steps; and (e) pages for the participant to write their plan for each week. Instructions for setting up and using the Fitbit Inspire 3 tracker and mobile app will be included. All materials serve as reference for discussions with the health coach.

Intervention Fidelity: We will use evidence-based MI training procedures identified in previous studies.^{50,51} The health coaches will receive an initial 1.5 days of in-person MI training by [name] (consultant, clinical psychologist). Prior to contacting participants, the coaches will complete 4 practice sessions, and receive feedback via 4 phone supervision sessions. [name] will code the sessions for MI fidelity by using the MI Treatment Integrity Coding System, version 4.1,⁵² and use this information during supervision sessions. During the study period (15 months), the health coaches will submit one audio recording and participate in one phone supervision per week (months 1-2), then per month (months 3-15). An intervention fidelity checklist will be created to assess the other intervention components, i.e., promoting and supporting self-efficacy, knowledge and skills, self-monitoring, autonomous motivation, and social support to become more active. With HSC Affiliate status, [name] will review the selected audio files saved to the secured P drive.

A Waitlist Control was selected to help boost recruitment and retention. Participants will be asked to maintain their usual lifestyle during the 12-week intervention. After the 12-week waitlist period, participants will receive (via mail) a Fitbit Inspire 3™ monitor and education materials, and the full telephone-based MI intervention with the health coach.

Retention: To enhance recruitment, retention, and adherence rates and to compensate participants for their time and offset phone data charges, a \$50 merchandise card will be provided for each outcome assessment (\$150 total). Additionally, both groups will be able to keep the Fitbit activity tracker after the study ends.

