		X					Reminder to ppt about assessment (text from [name] with link to Zoom or Skype videoconference session for physical function tests)
							Remote assessment conducted / completed via Skype or Zoom

PROTOCOL TITLE: Whole-of-Day Approach to Physical Activity in Older Cancer Survivors

Fees/ Postage	Phone		Email		Mail		
	IN	OUT	IN	OUT	IN	OUT	
		X					Follow-up for incomplete surveys; return of activPAL (see Assessment Call 4 Script ...)
						X	Mail gift card (after verifying activPAL returned, and remote assessment AND surveys completed)
						X	Mail letter to immediate intervention group (maintain usual activity; next study contact in 12 weeks)
							Start intervention for waitlist control participants (Fitbit setup, 5 health coaching calls)
							26-week assessment 
 • Schedule remote assessment w/ [name] via MYHealth calendar • Ask survey preference (mail/online)
							Repeat steps from 13-week assessment
							Post-study telephone survey

NOTES:

¹ Whoever conducts the consent process signs the participants' form once received; for e-consent; print consent form, sign, photocopy and keep one copy in the ppt's folder; mail a copy of signed consent to ppt

² Whoever conducts the consent process signs the participants' form once received; for e-consent; print consent form, sign, photocopy and keep one copy in the ppt's folder, mail a copy to ppt

PROTOCOL TITLE: Whole-of-Day Approach to Physical Activity in Older Cancer Survivors

Outcomes and Measurements

All measures have well-established validity and reliability, and are responsive to change.

Table 2. Outcomes & Measures (B=baseline; P=1-week post-intervention; F=3-months post-intervention follow-up to assess maintenance of behavior change & effects)(alpha=Cronbach's alpha; ICC=intraclass correlation test-retest reliability; RMSEA=root mean square error of approximation; CFI: comparative fit index)	B	P	F
Process Data (primary outcomes): As this is a feasibility and acceptability study, the primary outcomes relate to recruitment, retention, adherence, and adverse events, which will be carefully tracked. Collected and used to evaluate adherence: steps per day/number of active hours (downloaded from Fitbit® website), satisfaction with the program, likes & dislikes, barriers & issues, perceived degree of benefit, and intervention fidelity (see above)		X	X

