PROTOCOL TITLE: Whole-of-Day Approach to Physical Activity in Older Cancer Survivors

This intervention trial includes a 3 month follow-up assessment to evaluate whether the behavior change has been maintained (light-intensity physical activity, reduced sedentary activity), and whether the patient-reported outcomes have changed (e.g., quality of life, physical function and physical performance).

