PROTOCOL TITLE: Whole-of-Day Approach to Physical Activity in Older Cancer Survivors

classification of accelerometer data. Accelerometer methods will be published according to guidelines.⁸⁰⁻⁸²

Aim 1 - Feasibility & Acceptability: For this feasibility study, we hypothesize that we will meet the accrual target of 64 inactive, older cancer survivors within 18 months, retain 80% of the sample, and to achieve 80% adherence/fidelity to the intervention. No formal statistical analyses are needed for these hypotheses.

Aim 2 - Preliminary estimates of effect sizes: We hypothesize that physical function scores will improve in the intervention group compared to the control group. We will obtain means and precision estimates for between-arm differences in physical function scores at each time point. A linear mixed-effects model will be used with group, time, and group by time interaction, adjusted for ethnicity, rural/urban status, and baseline values as needed. The appropriate variance-covariance structure will be selected to account for the potential correlation among repeated measurements from the same participant. The primary test of interest is the group by time interaction, indicating whether there was a difference between groups in the primary outcome over time. Similar analyses will be conducted for secondary outcomes.

Aim 3 - Process evaluation: will be conducted via a mailed survey. Process data (**Table 2**) and other study related outcomes will be reviewed with the PAB to identify next steps and strategies to ensure the most appropriate design and methods for the future, larger RCT, with potential for broad dissemination and implementation.

PROTOCOL TITLE: Whole-of-Day Approach to Physical Activity in Older Cancer Survivors

Power / Sample Size Calculation

Using a 2-sided, 2-sample t-test, with a significance level of 0.05 and 25 people per arm, we will have 80% power to detect a mean difference of 8.1 in physical function scores (a large effect size) with a standard deviation of 10. To allow for 20% attrition, we plan to enroll and randomize 32 participants per arm. The results of the feasibility trial will inform the design (sample size, effect size) of a larger trial powered to examine efficacy

Maintaining Confidentiality

The following steps will be taken to secure the data and to maintain confidentiality:

- Study participants will be assigned a unique study ID.
- All data collected will be identified with the unique study ID.

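### The waitlist arm is treated before week 26, so the planned week-26 arm difference compares immediate with delayed start and cannot show maintenance

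*Combined protocol and SAP*

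**What the plan says.** Section 1.1, aim 1.1.b, sets effect-size targets for adoption (baseline to 12 weeks) and for maintenance (3 months post-intervention). For maintenance it says: "we hypothesize that the arm differences at 12 weeks will be sustained at 3-months post-intervention".

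Aim 2 in the Statistical Analyses part of section 10.0 carries this into the analysis: "We will obtain means and precision estimates for between-arm differences in physical function scores at each time point". It makes the group-by-time interaction of a linear mixed model the primary test. It does not say whether time is categorical or linear, which contrast is of interest, or how week 26 is to be read.

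The design sections describe what happens between the two later assessments:

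- Section 9.0, Waitlist Control: after 12 weeks of usual lifestyle, the control arm receives the Fitbit, the educational materials "and the full telephone-based MI intervention with the health coach".
- Section 3.2, last criterion: the Fitbit is worn "during weeks 14-26 if randomized to the delayed intervention arm".
- Section 9.0, Study Flow: the step "Start intervention for waitlist control participants (Fitbit setup, 5 health coaching calls" stands after the 13-week assessment and before the 26-week one.
- Section 9.0, Table 3: for weeks 14-25 the immediate arm's entry is "Maintain goals (no study contact".
- Section 9.0, Table 2: the last visit is defined for both arms alike as "F=3-months post-intervention follow-up to assess maintenance of behavior change & effects".
- Section 9.0, closing paragraph of Outcomes and Measurements: the trial includes "a 3 month follow-up assessment to evaluate whether the behavior change has been maintained".

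**The concern.** An arm difference measures the intervention's effect only while one arm is untreated. That holds up to week 13. By week 26 the waitlist arm has begun, and may have finished, its own course, while the immediate arm has been without contact.

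The two parts of hypothesis 1.1.b therefore pull against each other. If the intervention works, the waitlist arm should improve between weeks 13 and 26 and the arm difference should shrink. For the difference to be sustained, the waitlist arm would have to gain little or the immediate arm would have to go on improving. The hypothesis can fail when maintenance is perfect. A difference that remains is no clearer: it fits partial catch-up or further gain in the immediate arm, and does not show that the intervention failed in the waitlist arm.

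Maintenance is one of two effect-size targets in a primary aim, and section 10.0 says the results will inform the sample size and effect size of a larger trial. A week-26 difference read as maintenance would carry the wrong quantity into that design.

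**Working it through.** **Inputs from the plan** (section 10.0, Power / Sample Size Calculation): two-sided alpha 0.05, 25 evaluable per arm, SD 10, detectable difference 8.1, 20% attrition, 32 randomized per arm. Assessments are at weeks 1, 13 and 26 (section 3.2).

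**Assumed, not in the plan:** the share *m* of the week-13 effect that the immediate arm keeps at week 26; the share *g* that the waitlist arm gains by then; and the correlation *r* between visits (0.5 or 0.7, compound symmetry). The value 8.1 is what the plan can detect, not a projected effect.

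**Step 1. The plan's own figure.** SE = 10 × √(2/25) = 2.83. The noncentral t with 48 df gives 80.1% power for 8.1, and 25/0.8 = 31.25, rounded up to 32 per arm. The calculation reproduces. It covers one comparison of two groups and claims nothing for week 26.

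**Step 2. How far the waitlist arm could get.** No waitlist call dates are given. In the immediate arm, Fitbit baseline data are collected in week 2 and the calls fall in weeks 3, 5, 7, 9 and 11. If the waitlist arm keeps this spacing from week 14 (an assumption; shift 14 − 2 = 12 weeks), its last call falls in week 11 + 12 = 23, before the final assessment. A large *g* cannot be excluded, so the whole range is shown.

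**Step 3. Expected week-26 difference.** With week-13 effect *d*, the immediate arm stands at *m·d* and the waitlist arm at *g·d*. The difference is (*m* − *g*)·*d*, which falls short of the maintained effect *m·d* by *g·d*. For *d* = 8.1 and *m* = 1:

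| *g* | Week-26 difference | t-test power |
|---|---|---|
| 0% | 8.1 | 80% |
| 25% | 6.1 | 56% |
| 50% | 4.05 | 29% |
| 75% | 2.0 | 11% |
| 100% | 0 | 5% |

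The difference does not identify *m*. A value of 4.05 arises from (*m*, *g*) = (1, 0.5), (0.75, 0.25) or (0.5, 0). A value of 0 arises from (1, 1), (0.5, 0.5) or (0, 0).

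**Step 4. The group-by-time test.** The arm differences at weeks 1, 13 and 26 are 0, 8.1 and (1 − *g*) × 8.1. Because the plan does not state the time coding, both codings are shown (categorical: F with 2 and 96 df; linear in weeks: t with 96 df).

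| *g* | Categorical, r = 0.5 | Linear, r = 0.5 | Categorical, r = 0.7 | Linear, r = 0.7 |
|---|---|---|---|---|
| 0% | 84% | 80% | 97% | 95% |
| 25% | 75% | 55% | 93% | 77% |
| 50% | 72% | 28% | 91% | 42% |
| 75% | 75% | 10% | 93% | 13% |
| 100% | 84% | 5% | 97% | 5% |

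The categorical test keeps its power but does not address maintenance. At r = 0.5 the covariance matrix of the two change contrasts has 8 on the diagonal and 4 off it. The noncentrality is then 8 × 8.1²/48 = 10.9 whether the week-26 difference is 8.1 or 0. Full maintenance with full catch-up and total loss with no catch-up give the same three arm differences (0, 8.1, 0), so the test cannot separate them.

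**Step 5. What is intact.** The group contrast in baseline-to-week-13 change has 81% power (r = 0.5) or 96% (r = 0.7) for every *g*.

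**The case against.** This is a feasibility pilot. Table 2 says its primary outcomes relate to recruitment, retention, adherence and adverse events, and Aim 2 offers preliminary estimates only. No power is claimed at week 26, the week-13 contrast is sound, and a mixed model with group, time and their interaction already contains each arm's course. Anyone who looks at the immediate arm's means at weeks 13 and 26 can tell full maintenance from total loss. The stated purpose of the follow-up visit also fits that within-arm reading.

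All of this is true, and it shows why the repair is cheap. It does not make the text right. Aim 1.1.b speaks of arm differences and Aim 2 of between-arm estimates, and neither names a within-arm contrast. Physical function is also labelled a primary outcome (section 8.0 and Table 2).

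A second objection is that the interaction powers depend on the model. Asking for arm differences at each time point fits categorical time better than linear. If baseline enters as a covariate, which Aim 2 allows as needed, and only weeks 13 and 26 are outcomes, the interaction tests the change in the arm difference between those weeks. Its power is then about 5/11/29/56/80% for *g* = 0/25/50/75/100% (r = 0.5, *m* = 1, 48 df), the reverse of the linear pattern. This stands: the linear column shows one permitted reading, not a declared analysis. It also strengthens the case for naming the coding and the contrast, since no version of the test recovers maintenance.

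**Conclusion.** The concern holds. The maintenance hypothesis in aim 1.1.b cannot be answered by the planned week-26 arm difference, because that difference is (*m* − *g*)·*d* and *g* is unknown. With full maintenance of 8.1 points it can lie anywhere from 8.1 down to 0 as waitlist uptake goes from 0 to 100%. The unstated time coding can leave the primary interaction test with 84% power or with 5% at full catch-up (r = 0.5).

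That no untreated control exists at week 26 follows from the documents alone. The sizes rest on assumed values of *m*, *g* and *r*, compound symmetry, and 8.1 as an illustrative effect. The sample-size calculation and the baseline-to-week-13 comparison are not affected. Since a primary-aim hypothesis is at stake, this should be corrected before analysis.

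**What to change.** - **Aim 1.1.b:** delete or reword the statement on sustained arm differences.
- **Aim 2:** code time as categorical. Name the group difference in baseline-to-week-13 change as the primary contrast, and as the only comparison of intervention with untreated control.
- **Maintenance:** define it as the immediate arm's week-13-to-26 change, with its baseline-to-26 change alongside. Take both from the same model with 95% CIs and label them uncontrolled.
- **Waitlist arm:** report its week-13-to-26 change as a within-arm replication of adoption.
- **Week-26 arm difference:** if reported, label it immediate versus delayed start, not efficacy or maintenance. Change the visit label in Table 2 so that it separates the arms.

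These are text changes, although naming the contrast does narrow the stated primary test. The planned model with categorical time yields every quantity. No new data or participants are needed, and the waitlist design, chosen to help recruitment and retention, stays.

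The price is that maintenance is openly a single-arm estimate of modest precision. With 25 completers the 95% CI half-width is t(24) × 10 × √(2(1 − r))/√25. That is 2.064 × 10/5 = 4.1 points at r = 0.5 and 3.2 at r = 0.7 (about 4.0 and 3.1 with the model's 96 df). A controlled estimate would need an arm still untreated at follow-up, which is a question for the definitive trial.

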1.2. Secondary Aim

1.2.a. Conduct a process evaluation using mailed surveys and intervention fidelity assessments to inform a larger definitive trial, and more broad dissemination and implementation.

2.0 Background

The unprecedented growth of the U.S. older adult population (≥ 65 years), the cancer burden in this age group ($\geq 50\%$ of diagnoses) and the high survival rate ($\geq 80\%$),¹ is resulting in a rapidly expanding high-need population. Compared to the general population, older cancer survivors are at higher risk for physical function decline and other comorbidities (e.g., cardiovascular disease, osteoporosis), which further exacerbate the risk for functional limitations.²⁻⁵ Given the adverse consequences of functional impairment, including mobility limitations, increased number of falls, hospital/ nursing home admissions, diminished quality of life, premature death, and substantial financial costs,⁶⁻⁹ the importance of implementing strategies to delay or mitigate these effects is crucial. Despite being the majority of cancer survivors, few health behavior change interventions are conducted in older survivors with comorbidities.¹⁰

Regular physical activity has been shown to reduce the risk of these comorbid conditions,¹¹ yet $<30\%$ of cancer survivors meet the recommended goal (≥ 150 minutes/week of moderate-to-vigorous physical activity [MVPA]; e.g., fast walking, aerobics).¹²⁻¹⁴ Compounding the effects of

PROTOCOL TITLE: Whole-of-Day Approach to Physical Activity in Older Cancer Survivors

physical inactivity are the adverse physiologic distinct effects of sedentary behavior [SB].^{15,16} SB is defined as prolonged sitting or reclining with minimal energy expenditure.^{17,18} SB is associated with increased risk of cardiovascular disease,¹⁹⁻²² premature mortality,^{23,24} and decreased physical function,^{25,26} even among individuals who meet recommended activity guidelines.

To date, the predominant focus in physical activity research (including in cancer survivors) has been MVPA, since this intensity level has been found to confer the greatest health benefits.¹¹ However, older cancer survivors with physical functional impairment may have different needs, preferences, and barriers to being physically active, and thus require a different approach. Light-intensity activities ([LPA]; e.g., leisurely walking, gardening) are associated with better physical health,²⁷ including physical function^{28,29} and cardio-metabolic biomarkers,³⁰⁻³⁴ and better emotional well-being,^{27,35} independent of MVPA. Changing the focus from MVPA to LPA represents a more achievable and sustainable target for vulnerable populations such as older survivors with comorbidities. Despite emerging evidence of the health benefits of LPA, few rigorously designed RCTs have been conducted to evaluate the effects of LPA on physical and psychosocial health and well-being.

The majority of physical activity studies have been clinic- or center-based, focused on common cancers (breast, prostate, & colorectal), and targeted behavior.^{36,37} Few studies have focused on adults over 65 years or minority survivor populations (race-ethnic minorities, rural), and targeted outcomes meaningful to survivors (e.g., patient-reported outcomes).³⁶ Thus, there is a critical need for lifestyle activity interventions that are effective, low-cost, and accessible to older cancer survivors from diverse backgrounds, designed to be feasible, relevant, and meaningful for them. A home-based approach (both intervention delivery and outcomes assessment), expands the reach to underserved and underrepresented minority survivor populations.

We propose a home-based intervention focused on increasing light-intensity activity and reducing sedentary behavior throughout the day – more obtainable goals – for maintaining and improving physical function in vulnerable populations. By reducing barriers to participation, a home-based approach will expand the reach to underserved cancer survivors who are older or from rural areas.

